In Stage 1 of the project, we will employ a combination of qualitative methods, such as ethnographic observations at maternity facilities covering the antenatal care areas as well as the labour ward, in-depth interviews with 20-25 pregnant women (aged ≥16 years) temperature monitoring which will take place at the women's homes, semi-structured key informant interviews with 15-20 community stakeholders. Additionally, we will conduct personal and household temperature monitoring, and health facility, community and household thermal modelling with performance simulations to complement and enhance the insights gathered through qualitative approaches. Outputs from state 1− the formative study will support the codesign activities of the HAPI project. We will host workshops with relevant stakeholders to codesign a set of interventions to mitigate the impacts of heat on pregnant and postpartum women in Zimbabwe. Data collected in this study will be shared with stakeholders when coproducing interventions. Study results will be disseminated among study participants, local, provincial and national government officials, advocacy groups, and researchers to support policy changes.

In Stage 2 of the study, the thermal measurements will be combined with the qualitative work to inform complex interventions in households and health facilities. Specifically, we will pilot test the selected ad prioritised interventions from the codesign process using action-research and quasi-experimental pre-post intervention study. Action research involves "Observing-Reflecting-Planning-Acting" to inform intervention optimisation throughout implementation, in terms of feasibility, acceptability and operational performance. The single-arm quasi-experimental pre-post intervention study will be used to evaluate intervention feasibility, processes, scalability, pilot-effectiveness, and health and social outcomes. In Zimbabwe, we will recruit pregnant women between 26- and 30-weeks' gestation, with follow-up to 3-10 day postpartum, attending antenatal care services at in Mt Darwin District for both the pre- (n=400) and post- (n=400) intervention cohorts, separately (total n=800). A subset of women will be selected from the pre- (n $\sim$ 30) and post- intervention (n $\sim$ 60) cohorts (total n $\sim$ 90), to pilot selected individual and household interventions and community level interventions in the post intervention stage. We

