### 11. QUASI-EXPERIMENTAL PRE-POST INTERVENTION STUDY.

We apply a quasi-experimental pre-post-intervention design to evaluate intervention feasibility, processes, scalability, pilot-effectiveness, and health and social outcomes. In Zimbabwe, 400 women attending antenatal clinics at weeks 26-30 weeks of gestation will be enrolled before and then during intervention (named 'post-intervention cohort') (total n=800), and assessed four-weekly during pregnancy at routine clinic visits, and subsequently at childbirth and postpartum (planned within 72 hours). Semi-structured questionnaires will be administered to collect data on socio-economic status, heat impacts, behaviours related to heat and hydration, access to safe water, heat-resistance of dwellings, indigenous coping strategies, preferences around intervention attributes, intervention rankings, critical uncertainties, costs of service access and intervention participation, and implementation challenges (See appendix 31) We will also conduct biomedical assessments (ultrasound, blood and urine samples), and screening of wellbeing and for mental health conditions. Additional data will be extracted from the patient-held antenatal cards and birth records. Outcomes in the pre-intervention cohort of women will be compared with women in the post-intervention cohort.

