### 11.1.6. Participant sampling

*Pre- and post-intervention cohorts*: Consecutive eligible women in Mt Darwin District health facilities will be approached for recruitment. Consecutive recruitment minimises selection biases. We will enrol at least 5-10 women per day, with each cohort including up to 400 women (up to 400 pre-intervention and up to 400 post-intervention). Duration of total planned follow up time is about 2-4 months for each woman, assuming that most women complete pregnancy at around 40 weeks gestation. Routine clinical follow-up visits at antenatal clinic are generally at 20-, 26-, 30-, 34-, 36-, 38-, and 40-weeks during pregnancy (+/- 7 days), then during the first stage of labor, and again postpartum within 72 hours postpartum (window closes 10 days after delivery). Pre- and post-intervention cohort recruitment is spaced around 9-12 months apart and timed to coincide with the hot season.

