#### 11.1.9. Data collection

Data collection will occur at enrolment (26-30 weeks), and at a 4-week antenatal care follow-up visit visit , at childbirth and within 72 hours postpartum. These visits coincide with the MoHCC Basic Antenatal Care Visit Schedule for pregnant women . Informed consent will be conducted on the day of enrolment, following procedures described above and in further detail in Section 31. Contact details including telephone numbers, alternate telephone numbers and home address will be collected and logged separately from the database that captures study information

The first interview will take place during the summer months (between November 2024 - February 2025) with follow-up interviews conducted over the remainder of the hotter season, as per the schedule below(figure 9). Ideally pre-intervention cohort visits will be conducted from November 2024 to May 2025 and post-intervention cohort visits will be conducted from November 2025 to May 2026.

All interviews will be carried out by a research staff member and HCWs trained in conducting interviews and collecting study biomarkers. Enrolment semi-structured questionnaires will be interviewer-administered via CAPI (computer assisted personal interviewing) using a study tablet computer to collect data variables such as demographics, socioeconomics, housing type, water and electricity access, heat-related knowledge, current impacts of heat, behaviors related to heat and hydration, housing characteristics, and knowledge and use of indigenous coping strategies. Follow-up visit interviewer-administered questionnaires will be shorter and focus on heat-related knowledge, current impacts of heat, behaviors related to heat and hydration, use of indigenous coping strategies, access to safe water with post-intervention

postpartum questionnaires also including questions on preferences around intervention attributes, intervention rankings, critical uncertainties, costs of service access and intervention participation, implementation challenges, and reflections on the process of participating in this study. Questionnaires and interviews will be conducted in the language of participants' choice (but restricted to languages spoken fluently by the interviewers in our team).

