#### 18.1.2. Data Analysis

Evaluation of complex interventions involves consideration of a wide range of outcomes. For purposes of sample size, the primary pilot-effectiveness outcome is mild-moderate hypovolemic maternal dehydration during labour (urine specific gravity >1.015, measured by handheld optical refractometer, Sper Scientific portable clinical refractometer 300005). This reflects hydration practices, and heat exposure (fluid loss through perspiration). Secondary outcomes include process indicators for interventions, heat strain, mental wellbeing, composite maternal-clinical outcomes (obstetric emergencies, emergency Caesarean section, pre-eclampsia/eclampsia, antepartum or postpartum haemorrhage, and sepsis) and composite infant clinical-outcomes (preterm birth, low birth weight, APGAR score ≤6, and neonatal admission). Household temperatures will be used to determine effectiveness of household level interventions.

Baseline survey data will be analysed descriptively using percentages and presented in tables and will be included in reports and publications as such. Survey baseline and follow-up data will be compared using Student's t test, Mann-Whitney U test and chi-square, as applicable. Analyses will be presented overall, and by site, facility, and pre-specified population subgroups (to identify high-risk groups). Binomial multivariable regression will compute risk differences between pre- and post-measures in the primary outcome, controlling for multihazard factors and changes in climate exposures over time, with fixed-effect clusters. If size or direction of effectiveness differs markedly between facilities, or sites then analysis may be restricted to facility- or site-level.

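### Climate adjustment is specified for the primary outcome only; heat-sensitive survey outcomes are to be compared by unadjusted tests, so a hotter or cooler second year can show or hide an effect of the package

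*Protocol*

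**What the plan says.** Section 18.1.2 (Data Analysis) names two inferential procedures. For the primary outcome, dehydration in labour, a binomial multivariable regression with fixed facility or site effects will give "risk differences between pre- and post-measures in the primary outcome, controlling for multihazard factors and changes in climate exposures over time". For the questionnaire data, "Survey baseline and follow-up data will be compared using Student's t test, Mann-Whitney U test and chi-square, as applicable". The section lists the other outcomes: "Secondary outcomes include process indicators for interventions, heat strain, mental wellbeing, composite maternal-clinical outcomes", followed by an infant composite. It names no adjusted model for any of them, and no other section extends the climate adjustment beyond the primary outcome.

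The design has no concurrent control. The summary (section 4) says: "The single-arm quasi-experimental pre-post intervention study will be used to evaluate intervention feasibility". Section 11 sets the comparison: "Outcomes in the pre-intervention cohort of women will be compared with women in the post-intervention cohort". Section 11.1.6 gives the timing: "Pre- and post-intervention cohort recruitment is spaced around 9-12 months apart and timed to coincide with the hot season".

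According to section 11.1.9, the enrolment questionnaire covers, among other items, "heat-related knowledge, current impacts of heat, behaviors related to heat and hydration, housing characteristics". Wellbeing and mental health are also screened.

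**The concern.** With no concurrent control, anything that differs between the two hot seasons is mixed with the intervention. Weather is an obvious candidate, and the protocol treats it as one: section 11.1.5 says that the level of dehydration varies with ambient temperature and season, and section 18.1.2 adjusts the primary outcome for it. The same reasoning applies to questionnaire outcomes that respond to heat, such as reported heat impacts, drinking and heat-protective behaviour, and probably wellbeing. For these the protocol fixes tests that cannot adjust. A cooler second year could then look like benefit, and a hotter one could cancel a real benefit.

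Section 18.1.2 also does not define baseline and follow-up for the survey data. They could mean the pre and post cohorts. They could also mean the enrolment and later questionnaires within a cohort, since section 16 lists a Baseline and a Follow-up Questionnaire for both cohorts. On that second reading the pre cohort is no longer the comparator, and the post cohort's baseline is measured in women who already live with the intervention.

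Health and social outcomes are a stated purpose of Stage 2 (sections 7.1 and 10), so the estimates at stake are ones the study means to report.

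**Working it through.** **Inputs.** Section 11.1.5 gives about 800 women (400 per cohort), 15% attrition, a 15% difference, power above 95%, and 30-60% dehydration in the before cohort. After attrition, n = 400 × 0.85 = 340 per cohort. The significance level is not stated, so two-sided 5% is assumed.

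**Reproducing the plan's figure.** For proportions p1 and p2 with difference d and mean p̄:

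- SE0 = √(2p̄(1−p̄)/n)
- SE1 = √((p1(1−p1) + p2(1−p2))/n)
- power ≈ Φ((|d| − 1.96·SE0)/SE1)

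For 45% v 30%: SE0 = √(2 × 0.375 × 0.625/340) = 0.0371, SE1 = √((0.2475 + 0.21)/340) = 0.0367, and (0.15 − 0.0728)/0.0367 = 2.11, so power is 98.2%. For 30% v 15% it is 99.7%, and for 60% v 45% it is 97.6%. The stated figure holds across the range if 15% is read as an absolute difference.

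**A weather shift with no intervention effect.** The same test rejects with probability Φ((−1.96·SE0 − d)/SE1) + 1 − Φ((1.96·SE0 − d)/SE1), where d is now due to weather alone. For 30% v 35%: SE0 = 0.0359, SE1 = 0.0359, and (0.0704 − 0.05)/0.0359 = 0.57. The upper tail is 28.5% and the lower tail is negligible. Over starting rates of 30%, 45% and 60%, with shifts in either direction:

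| Assumed weather shift | Nominally significant chi-square |
|---|---|
| 0 points | 5% |
| 3 points | 12-14% |
| 5 points | 26-31% |
| 10 points | 74-86% |

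For a t test on a continuous score, the standard error of the difference in SD units is √(2/340) = 0.0767. A shift of 0.1 SD gives 0.1/0.0767 = 1.30, and Φ(1.30 − 1.96) = 26%. A shift of 0.2 SD gives 74%.

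**Masking.** Take a true 15-point reduction from 45%. The chance of a significant result is 98% with no weather shift. It falls to 76% if the second year's weather adds 5 points, and to 26% if it adds 10.

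The documents give none of these shift sizes. The 30-60% starting range belongs to the primary outcome, and it is borrowed here only because no rate is given for any survey outcome.

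**Timing of the post cohort's baseline.** Section 11 enrols this cohort during the intervention. Table 1 in section 11.1.10, headed as an example schedule, starts the intervention on 1 June 2025 and post-cohort enrolment on 15 January 2026: 228 days, or 7.5 months. Section 11.1.9 has post-cohort visits from November 2025. From 1 June to 1 November is 153 days, or 5.0 months. Either way the enrolment value is not an unexposed one.

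**The two readings side by side.**

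- *Pre cohort v post cohort.* This fits section 11 and the choice of tests, since Mann-Whitney U and the ordinary chi-square compare independent groups. Differences in weather between years then go uncorrected.
- *Enrolment v later visits within a cohort.* This fits the questionnaire names in section 16. In the post cohort, effects reached before enrolment drop out of the comparison, while changes with season and gestation stay in.

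The two problems belong to alternative readings and would not occur together.

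**The case against.** The strongest reply has four parts.

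1. *The unadjusted sentence covers survey data only.* This stands. The maternal and infant composites come from pregnancy and birth records, and section 18.1.2 names no test for them. A reader might infer that they too will be analysed without adjustment, but the protocol does not say so, and their model may properly sit in the SAP.

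2. *Both cohorts are recruited in the hot season, and the rejection rates rest on assumed shifts.* This stands in part. Same-season timing removes much of the seasonal difference, so the 30-60% range cannot be read as year-to-year variation. A reader might take 26-31% as this study's false-positive rate. It is not: it shows only how a study of this size responds to a modest uncorrected shift. But recruiting in the same season does not make two years equally hot.

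3. *Section 11 fixes the pre cohort as comparator, so the within-cohort reading is strained.* This largely stands. That reading is the less natural one, and the point there is mainly undefined wording. A reader might also infer that a late baseline would be credited as package effect. The direction is the opposite: an exposed baseline dilutes the effect.

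4. *Not every survey item is sensitive to weather, and climate terms do not remove other rival explanations.* This stands. Acceptability of the intervention, for example, has no obvious link with the year's weather, and climate terms would not deal with HIGH Horizons activity in facilities of the same district. It is a reason to limit the change to heat-sensitive outcomes, not a reason against it.

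The reply does not meet the central fact. The protocol ties climate control to one outcome and names unadjusted tests for the survey data. That is a stated method, not a detail left open.

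**Conclusion.** The point holds in this limited form. Section 18.1.2 fixes unadjusted tests for survey outcomes, some of which depend on heat, in a single-arm comparison of cohorts 9-12 months apart, and it reserves climate adjustment for the primary outcome. An unadjusted pre v post comparison of those outcomes can show or hide an effect because of the weather.

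The actual size is unknown. With 340 per cohort, a two-sided 5% test, starting rates of 30-60% and no true effect, an assumed 5-point shift would be nominally significant in about 26-31% of studies. The further fault is that baseline and follow-up are undefined. On the within-cohort reading the post cohort's baseline comes about 5 to 7.5 months into the intervention, and any effect would be diluted.

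The finding does not show a wrong analysis of the clinical composites, and it does not touch the primary analysis. The change should be made, because a better method is already in the protocol and the data for it are already planned.

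**What to change.** In section 18.1.2:

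- State that effect estimates for heat-sensitive secondary and survey outcomes compare the pre- and post-intervention cohorts at the same visit. Use the primary outcome's regression approach (binomial for binary outcomes, linear for continuous ones) with ambient climate exposure and facility terms. Ambient here means outdoor: ceilings and cool roofs are meant to change indoor temperature, so adjusting for that could remove part of the effect.
- Name the outcomes that count as heat-sensitive.
- Define baseline and follow-up. Keep the t, Mann-Whitney and chi-square tests and any within-cohort change as description, and do not treat the post cohort's enrolment value as an unexposed baseline.
- Say that the record-based clinical composites follow the same approach. This is for consistency, since no wrong test is stated for them.

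The cost is protocol or SAP wording, a little more analysis and slightly wider intervals for the adjusted outcomes. Weather-station and remote-sensing data, facility and questionnaire responses are already to be collected (section 11.1.9 and Table 1).

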### 11.1.4. Exclusion criteria

 Women in the pre-intervention cohort will be excluded from the post-intervention quasi experimental cohort.

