### 11.1.5. Sample Size

For the purposes of determining the required sample size, the primary pilot-effectiveness outcome is mild-moderate hypovolemic maternal dehydration during labour (urine specific gravity >1.015, measured by handheld optical refractometer, Sper Scientific portable clinical refractometer 300005 or similar). This reflects both hydration practices, and heat exposure (fluid loss through perspiration). We calculated the sample size to provide sufficient power for country-specific analyses; a pooling across countries may not be possible due to heterogeneity in intervention package and effectiveness. With about 800 women and 15% attrition, we will have >95% power to detect a 15% difference in the proportion of women with primary outcome between the pre- and post-intervention cohorts. In the before cohort, based on a literature review, we estimated 30-60% of women will have mild-moderate dehydration during labour (level varying by ambient temperature and season).

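### The primary pre-post model names environmental and cluster adjusters but no characteristic of the woman, so a measured case-mix shift between the two cohorts would enter the intervention estimate

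*Protocol*

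**What the plan says.** Section 4 of the protocol describes the design: "The single-arm quasi-experimental pre-post intervention study will be used to evaluate intervention feasibility". Section 11 gives the contrast: "Outcomes in the pre-intervention cohort of women will be compared with women in the post-intervention cohort". Section 11.1.4 makes the two samples distinct: "Women in the pre-intervention cohort will be excluded from the post-intervention quasi experimental cohort". Section 11.1.6 spaces recruitment of the cohorts around 9 to 12 months apart, both in the hot season, and states: "Consecutive recruitment minimises selection biases".

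For the primary outcome (urine specific gravity above 1.015 in labour), Section 18.1.2 plans a binomial model that estimates the risk difference between the cohorts. The adjustment it names is: "controlling for multihazard factors and changes in climate exposures over time, with fixed-effect clusters". The same section describes baseline survey data in percentages, compares survey data with unadjusted tests (t test, Mann-Whitney, chi-square) and presents results by population subgroup. It does not link any characteristic of the woman to the primary model.

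On data available, Section 11.1.9 says the enrolment questionnaire will "collect data variables such as demographics, socioeconomics, housing type, water and electricity access". It also lists prior pregnancy history and information to determine gestational age among the items extracted from records. Section 11.1.7 records age in the screening log.

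**The concern.** With a single arm and separate cohorts, the period coefficient is the intervention estimate, and no woman serves as her own control. Whatever differs between the cohorts and is not in the model goes into that coefficient. The named adjusters describe the environment and the cluster. Consecutive recruitment limits selection within a cohort. It does not make the women of two calendar years alike in age, parity or socio-economic position.

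The protocol itself gives a reason why case mix might move. Eligibility requires an intention to deliver in district facilities (Section 11.1.3), and the outcome is measured in labour. Before and during enrolment of the second cohort, the project repairs ceilings in maternity and postpartum wards, installs water tanks and solar power, and runs radio messages, heat champions and chief-led engagement (Sections 12.1.2 and 12.1.8). These could change who books and delivers at the study facilities. Section 18.1.3 treats only reporting bias, and Section 28 does not mention change between the cohorts.

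At stake is whether a change in who was enrolled is reported as pilot effectiveness, or masks a real effect.

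**Working it through.** **Inputs from the protocol.** 800 women in total, 400 per cohort; 15% attrition; pre-intervention rate 30% to 60%; target difference 15% (Sections 11.1.5 and 11.1.6). Analysed per cohort: 400 × (1 − 0.15) = 340. Alpha is not stated; two-sided 0.05 is assumed.

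**Formula.** For rates p1 and p2 with n per cohort, d = |p1 − p2| and p̄ = (p1 + p2)/2:

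- SE0 = √[2p̄(1 − p̄)/n] and SE1 = √[(p1(1 − p1) + p2(1 − p2))/n]
- rejection probability = Φ[(d − 1.96·SE0)/SE1] + Φ[(−d − 1.96·SE0)/SE1]

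**Step 1: the plan's own figure.** The protocol states: "With about 800 women and 15% attrition, we will have >95% power to detect a 15% difference in the proportion". With an absolute fall of 15 points and n = 340:

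| Pre-intervention rate | Power |
|---|---|
| 30% | 99.7% |
| 45% | 98.2% |
| 60% | 97.6% |

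The figure reproduces and is not in dispute. If the 15% were a relative reduction, power would be only 26% to 66%, so the absolute reading must be meant. The calculation takes the cohorts as comparable; a larger sample does not reduce a bias.

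**Step 2: false positives under an assumed case-mix shift.** Suppose the intervention does nothing, but case mix lowers risk by d in the second cohort. Example at 45% with d = 0.02: SE0 = SE1 = 0.0381. The two terms are Φ(−1.43) = 0.076 and Φ(−2.49) = 0.006, which sum to 8.2%. Across 30% to 60%:

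| Assumed shift in risk | False-positive rate |
|---|---|
| 2 points | 8.2–8.9% |
| 2.5 points | 10.1–11.1% |
| 3 points | 12.4–14.0% |
| 5 points | 26.2–31.0% |

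**Step 3: what produces such a shift.** For one unadjusted binary trait, bias = (change in prevalence between cohorts) × (risk difference for the trait). The documents give neither term; the values below are assumptions. Rates are at 45% and n = 340.

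| Prevalence change | Trait risk difference | Bias | False-positive rate |
|---|---|---|---|
| 5 points | 10 points | 0.05 × 0.10 = 0.5 points | 5.2% |
| 10 points | 20 points | 0.10 × 0.20 = 2.0 points | 8.2% |
| 20 points | 20 points | 0.20 × 0.20 = 4.0 points | 18% |
| 20 points | 30 points | 0.20 × 0.30 = 6.0 points | 35% |

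**Step 4: does adjustment help?** A simulation used 4,000 replicates, a linear risk-difference model with robust standard errors, base risk 35% and no intervention effect. The trait carried a 25-point risk difference and had 50% prevalence in one cohort and 40% in the other. Unadjusted, the bias was 2.6 points and the false-positive rate 10.2%. With the trait in the model, the bias was 0.1 point and the rate 5.2%. The simulation had no facility or climate terms, so it shows the mechanism and not the performance of the planned model.

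**The case against.** The strongest reply is that Section 18.1.2 does not call its list exhaustive, that multihazard factors are undefined and might include household items, and that exact covariates are commonly settled in a statistical analysis plan, which is not shown here. This limits the point but does not remove it. The protocol does not defer the adjustment set: it names one for its primary model, and an analysis plan that follows it inherits the omission.

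A reader might infer that any change between the two years is credited to the intervention, or that adjustment is the study's only protection. The documents do not support that. Both cohorts fall in the hot season and share eligibility criteria, including the 26 to 30 week window. Climate is adjusted. Cluster fixed effects (taken here to be facilities) absorb shifts in facility mix wherever a facility contributes to both cohorts.

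A reader might also infer that every useful covariate is already in hand. Demographics and socioeconomics are named only as groups. Neither education nor occupation is listed for the cohorts, and the baseline questionnaire (Appendix 31) is not in the text. Some candidates are also unsafe. The intervention includes guidance on scheduling work, self-help groups and cool roofs, so occupation, or a wealth index built on housing, water or electricity, could carry part of the effect.

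Finally, the shift sizes are pure assumptions. A 10-point prevalence change within about a year, in a trait with a 20-point risk difference, gives 2.0 points against a 15-point target. Smaller shifts do little harm.

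**Conclusion.** The point holds in a limited form. The primary model as written names no woman-level covariate, and the design compares different women about a year apart without a concurrent control. A shift in measured case mix that is not absorbed by facility, season or climate would therefore enter the risk difference.

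The documents do not show that such a shift will occur or how large it would be. For net shifts of 2 to 5 points in risk, the false-positive rate would be about 8% to 31%, assuming 340 independent women per cohort, two-sided 5% and no true effect. At 0.5 points it is 5.2%, essentially nominal. The stated power stands. This should be changed because the correction is cheap, and fixing the covariates now prevents a choice made after the data are seen. It would not turn the comparison into a controlled one: unmeasured year-to-year change stays in the estimate.

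**What to change.** In Section 18.1.2:

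- Add to the primary binomial model a short, fixed set of woman-level covariates that the intervention cannot plausibly change: maternal age, parity or prior pregnancy history, gestational age at enrolment and, if the baseline questionnaire records it, education.
- Use occupation or a wealth index only if measured so that the intervention cannot alter it (for example, status before pregnancy, with housing, water and electricity items left out). Otherwise keep them for a sensitivity analysis.
- State that enrolment urine specific gravity, hydration behaviour, heat knowledge and water access are not adjusters, because the second cohort is enrolled during the intervention and these may carry part of its effect.
- If the identity-link model does not converge, obtain the adjusted risk difference by marginal standardisation from a logistic model.

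In Section 11.1.6, limit the claim about selection bias to selection within a cohort. In Section 28, state that the adjusted difference is a before-after contrast and still includes unmeasured change between the years.

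The cost is a few sentences, a few degrees of freedom out of about 680 women (2 × 340), and a rule for occasional missing covariates. The core items need no new data collection.

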### 7. OVERALL STUDY SETTINGS

The study site rural Mount Darwin district in Mashonaland Central Province in Zimbabwe (see picture below) – pregnant women have few means of reducing heat exposure during a heatwave, and even drinking water may be scarce [61]. Health facilities, poorly-built brick households and informal housing in urban slums offer little to no protection

against heat exposure and are frequently 4-6°C warmer indoors than outdoors [10, 25] In Zimbabwe, primary data collection for Stage 1 of the study will occur at Chitse Clinic, Dotito Rural Health Clinic and Mount Darwin Hospital. Including multiple facilities and contrasting sites allows for assessment of how 'interventions interact with context' [62] within and between sites, and increases the potential transferability of the findings. Primary data collection for Stage 2 of the study will be conducted at Chitse Clinic, Dotito Rural Health Clinic, and Mount Darwin Hospital, and may extend to other rural facilities within the district within the catchment areas of these three primary sites.

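### The protocol lets the observed effect decide, with no defined threshold, whether the primary analysis is restricted to single facilities, although only the overall comparison is powered

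*Protocol*

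**What the plan says.** Section 18.1.2 sets the main analysis of the primary outcome: "Binomial multivariable regression will compute risk differences between pre- and post-measures in the primary outcome", adjusted for other hazards and for changes in climate exposure, with fixed effects for clusters. On reporting it says: "Analyses will be presented overall, and by site, facility, and pre-specified population subgroups (to identify high-risk groups". The section's last sentence then adds: "If size or direction of effectiveness differs markedly between facilities, or sites then analysis may be restricted to facility- or site-level".

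The sample size in Section 11.1.5 rests on the overall comparison within the country: "With about 800 women and 15% attrition, we will have >95% power to detect a 15% difference in the proportion of women", with a pre-intervention level given as "we estimated 30-60% of women will have mild-moderate dehydration during labour". The caution about heterogeneity in that section concerns pooling across countries. It does not mention facilities.

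Section 7 names three facilities ("Primary data collection for Stage 2 of the study will be conducted at Chitse Clinic, Dotito Rural Health Clinic, and Mount Darwin Hospital") and leaves room for more. Section 11.1.6 recruits consecutively, "each cohort including up to 400 women (up to 400 pre-intervention and up to 400 post-intervention", with no quota per facility.

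**The concern.** The closing sentence of Section 18.1.2 is a stated rule about the primary analysis, and it has three weaknesses.

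- The condition is the observed effect, so the level of analysis is chosen after the result is known.
- Nothing defines a marked difference: there is no test and no size.
- The restriction is optional even when the condition is met.

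Facility results are planned in any case. The sentence therefore adds something only if it lets facility results displace the overall one.

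At stake is the one comparison that the sample size supports. A null or diluted overall estimate could give way to separate facility estimates, of which one may look favourable by chance. Section 9 says that Stage 2 will guide decisions on scaling up, so such a result could have consequences.

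**Working it through.** **Inputs from the protocol.** 800 women in two cohorts of up to 400; 15% attrition, leaving 400 × 0.85 = 340 per cohort; a 15% difference, read as 15 percentage points; pre-intervention level 30-60%; three named facilities.

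**Assumptions, not in the protocol.** Two-sided alpha 0.05; exactly three facilities; equal thirds unless noted (340/3 ≈ 113 per cohort per facility); any facility with p<0.05 counts as a positive finding.

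**1. The stated power.** Power = Φ[(0.15 − 1.96·s0)/s1], where s0 = √(2p̄(1−p̄)/n) and s1 = √((p1(1−p1)+p2(1−p2))/n).

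- 30% to 15%, n = 340: s0 = 0.0320, s1 = 0.0315, z = 2.77, power 99.7%.
- 60% to 45%, n = 340: s0 = 0.0383, s1 = 0.0379, z = 1.98, power 97.6%.

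The figure of more than 95% is reproduced.

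**2. Power in one facility (same formula, n = 113).**

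- 30% to 15%: s0 = 0.0556, s1 = 0.0547, z = 0.75, power 77.4%.
- 60% to 45%: s0 = 0.0664, s1 = 0.0657, z = 0.30, power 61.8%.

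Unequal enrolment widens this. With a 60/20/20 split, the large facility (204 per cohort) has 86-96% and each small one (68) has 42-55%. With 70/15/15, the large one (238) has 91-98% and the small ones (51) have 33-44%.

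**3. Type I error of the switch.** Three independent tests at 0.05 give 1 − 0.95³ = 14.3%. The rule itself was simulated with no true effect: use the overall test unless the facilities differ markedly, and otherwise claim an effect if any facility has p<0.05. There were 400,000 trials for each of six scenarios (baseline 30%, 45% or 60%; equal or 60/20/20 split).

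| Meaning of a marked difference | Triggered under the null | Type I error |
|---|---|---|
| Heterogeneity p<0.05 | 5% | about 9% |
| Heterogeneity p<0.10 | 10% | 11-12% |
| Heterogeneity p<0.20 | 20% | about 14% |
| Opposite directions | about 70% | 14-15% |
| Range above 10 points | 47-61% | 15-16% |
| Range above 15 points | 21-32% | 14-15% |

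The overall test alone stays at 5%. The inflation is therefore 9/5 = 1.8-fold to 16/5 = 3.2-fold.

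**4. How often the trigger fires when the effect is real and uniform.** With a true 15-point effect at each of three equal facilities, opposite directions occur in only about 1-3% of trials. A range above 10 points occurs in about 38-52%, and above 15 points in about 14-26%. With a 60/20/20 split, opposite directions occur in about 2.5-6.5% and a range above 10 points in about 49-61%.

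**The case against.** Several arguments for the sentence have weight.

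- *Overall results are to be presented anyway.* Section 18.1.2 says so. But the later sentence allows the analysis to be restricted instead, and nothing says that the overall estimate stays primary or must still be reported. The two sentences need reconciling.
- *Restriction may mean showing every facility separately, not choosing one.* This is a natural reading, and the protocol nowhere says that one significant facility counts as success. The error rates above depend on that assumption. They also count a significant result in either direction. Counting only favourable results, three independent tests give 1 − 0.975³ = 7.3% against 2.5%, a similar ratio.
- *Effects may really differ.* Section 12.1.1 allows facility- and site-specific interventions, and Section 7 wants to study how interventions interact with context. That justifies reporting heterogeneity. It does not justify changing the primary analysis after the effects are seen.
- *This is pilot work, and tests and thresholds can sit in the SAP.* That is fair for details that the protocol omits. Here the protocol states the rule, and a SAP that followed it would carry it over.

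A reader might also infer that chance alone will usually trigger the switch whatever the truth. The calculations do not support that: under a uniform 15-point effect, opposite directions are rare, and a strict heterogeneity test fires in about 5% of null trials.

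**Conclusion.** The point stands as a defect in a stated rule. The primary analysis may be restricted to facility or site level on the strength of the observed effect, at discretion and without a threshold, while the sample size supports only the overall comparison.

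None of the readings of the trigger that were tested keeps the type I error at 5%. It lies between about 9% and 16%, given a two-sided alpha of 0.05, three facilities and a claim based on any significant facility. A flat statement that the false-positive rate triples would be too strong. That describes the looser readings (opposite directions, or a spread of 10 to 15 points); the strictest one tested a little less than doubles it.

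The 62-77% facility power is likewise conditional on three equal facilities. With unequal enrolment the smaller facilities would have less power and the largest more. Nor does the text show an intention to select a favourable facility. It leaves that possibility open.

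**What to change.** Replace the last sentence of Section 18.1.2 with a statement of two things:

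1. The overall risk difference between cohorts, adjusted for facility, is the primary result and is always reported, whatever the heterogeneity between facilities.
2. A cohort-by-facility interaction, and facility-specific risk differences with confidence intervals for all facilities, are reported as exploratory results that do not replace it.

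This also removes the tension with the earlier sentence on presenting results overall and by facility. It keeps the overall test at 5% with 97.6-99.7% power and loses no facility-level information. It costs one sentence and needs no further women or data. It should be settled before the cohorts are compared.

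Making the three facility tests confirmatory with a Bonferroni correction (0.05/3 = 0.0167 each) would also hold the error at 5%, but would leave only about 44-62% power per facility with equal thirds.
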